2. LAY SUMMARY

Our aim is to test whether we can predict if people with psoriatic arthritis (PsA) will respond to certain biologic drugs using blood tests. First, we will test if high levels of a type of T cells (activated Th17 cells) predict response to these treatments. Second, does combining this blood result with other laboratory tests or patterns of arthritis predict response more accurately? We will use statistical tests to estimate how effective these approaches are to select the biologic drug for each individual. If successful, this approach could ensure that patients receive their best option first, ensuring their disease is controlled more quickly and quality of life improved, while avoiding unnecessary drug use.

PsA is a type of inflammatory arthritis that develops in around 15% of people with the skin condition psoriasis, causing swollen and painful joints. It affects around 150,000 people in the UK. For patients who do not respond to standard arthritis drugs, two classes of biologic drugs are available (namely, TNF or IL-17A blockers). A similar proportion of patients respond to both with around 50% achieving a good response. However, we do not know how to predict in advance which patient will respond best to each of these drugs. A recent small study in Japan suggested that choosing the biologic drug based on patients' blood Th17 cells could give better results than the doctors' choice. However, they only did the blood tests in 28 people so we need to test this in a large study to see if this is reliable.

Patients with PsA about to start their first biologic will be invited to join the study. They will have a blood sample taken to analyse their T cells to see whether each patient has high or low levels of activated Th17

OPTIMISE_Protocol_V5.0_17Jun2022.docx

Clinical Research Protocol Template version 15.0

© Copyright: The University of Oxford and Oxford University Hospitals NHS Foundation Trust 2019

cells. The patients will be allocated equally to receive either TNF or IL-17 blocking biologics. We will measure how well they respond to the drug therapy after 6 months of treatment and test whether the initial blood result could have predicted their chance of responding.

If the test is able to predict the response to one or both of the drugs, we will then use statistical models to estimate how effective it would be if this blood test was used to choose the specific therapy. We will also combine this test with other blood results and the clinical pattern of a patient's arthritis to see if this further improves our ability to predict a good response.

3. SYNOPSIS

Study Title	Optimising Psoriatic Arthritis Therapy with Immunological Methods to Increase Standard Evaluation
Internal ref. no. / short title	OPTIMISE
Public Title	Can we predict which patients with Psoriatic Arthritis will respond to treatment using precision medicine?
Study registration	Registry name: ISRCTN registry
	Study identifier/ Registration number: ISRCTN17228602 Date of registration: 23 Mar 2021
Sponsor	RGEA, University of Oxford Joint Research Office, [name]
	E-mail: [contact]
Funder	National Institute of Health Research Efficacy and Mechanism Evaluation Grant NIHR 129023
Study Design	This is an open-label multi-centre, parallel-group, two arm randomised controlled study.
Study Participants	Adults (≥18 years old) with psoriatic arthritis confirmed by the CASPAR criteria who are planning to start biological therapy for their PsA following routine clinical practice.
Sample Size	424 (212 treated with TNF inhibitors, 212 treated with secukinumab)
Planned Study Period	01 December 2020 - 30 November 2024 Total study period - 48 months (9 months set up, 18 months recruitment, 6 months follow up, 15 months analysis and reporting). Each patient will be in the study for max 30 weeks (max 6 weeks screening to
	baseline + 24 weeks).
Planned Recruitment period	January 2022 to 30 June 2023

	Objectives	Outcome Measures	Timepoint(s)
Primary	To compare the response in participants with a high baseline CD4 T cell activated Th17 immunophenotype, compared to those with low baseline proportions on the clinical response to TNF and IL-17A inhibitor therapy in PsA.	Clinical response as measured by the minimal disease activity (MDA) criteria	Immunophenotype data at baseline and clinical response at week 24.
Secondary	To compare the response in participants with high intracellular IL17 levels, compared to those with low levels on the clinical response to TNF and IL- 17A inhibitor therapy in PsA.	Clinical response as measured by the minimal disease activity (MDA) criteria	Immunophenotype data at baseline and clinical response at week 12/16 and 24.
	To understand if the activated Th17 surface and intracellular signature resolves after treatment with IL-17A blockade and how it is altered after TNF blockade.	Activated Th17 proportion and intracellular levels of IL-17	Immunophenotype data at baseline and week 24.
	To understand if changes in the activated Th17 surface and intracellular signature differ in treatment responders and non-responders.	Clinical response as measured by the minimal disease activity (MDA) criteria.	Clinical disease pattern and Immunophenotype data at baseline and clinical response at week 12/16 and 24.
	To explore if the immune subset-specific transcriptomic signature can be used to predict response to IL-17A and TNF blocking therapies either alone or in combination with the activated surface and intracellular Th17 signatures.	Clinical response as measured by the minimal disease activity (MDA) criteria.	Clinical disease pattern and Immunophenotype data at baseline and clinical response at week 12/16 and 24.
	To explore if any of the baseline immune signatures are associated	Clinical response in PsA tissues including joint counts, enthesitis, dactylitis, skin and	Immunophenotype data at baseline and clinical

	with response in different PsA tissues	nail disease and in overall disease as measured by the PASDAS.	response at week 12/16 and 24.
	To explore if any of the baseline immune signatures are associated with response and disease impact from the patients' perspective	Response as measured by patient reported outcomes including PsAID, SF36 and WPAI	Immunophenotype data at baseline and clinical response at week 12/16 and 24.
	To use the immune subset-specific transcriptomic signature to identify a limited number to of transcriptomic biomarkers that can be validated in whole blood.	Cell specific transcriptomic data and whole blood transcriptomes	Immunophenotype data at baseline and week 24.
	To use the immune subset-specific transcriptomic signature to define the pathways driving biologic-refractory disease.	Cell specific transcriptomic data and whole blood transcriptomes	Immunophenotype data at baseline and week 24.
Intervention(s)	17A inhibitors (secukinuma both TNF inhibitors and IL-1 line biologics in PsA. Patier	with a biologic drug (TNF inhibitors b) in keeping with routine clinical p 17 inhibitors are licensed and NICE nts will be randomised in a 1:1 ratic ratified by baseline immunophenot	practice. At present approved as first to receive either
Comparator	See above		

4. ABBREVIATIONS

BMI	Body mass index
BSA	Body surface area
CASPAR	Classification Criteria for Psoriatic Arthritis
СІ	Chief Investigator
CRF	Case Report Form
CRP	C- reactive protein
СТИ	Clinical Trials Unit
DMARDs	Disease- modifying anti-rheumatic drugs
DSMC	Data and Safety Monitoring Committee
EME	Efficacy and Mechanism Evaluation
EULAR	European League Against Rheumatism
FBC	Full blood count
GCP	Good Clinical Practice
GP	General Practitioner
HAQ	Health assessment questionnaire
HIV	Human immunodeficiency virus
HRA	Health Research Authority
ICF	Informed Consent Form
IL-17	Interleukin 17
IL-17A	Interleukin 17A
IL-17Ai	Interleukin 17A inhibitors
LEI	Leeds enthesitis index
LFT	Liver function test
MAIT	Mucosal associated invariant T cells
MDA	Minimal disease activity
NICE	National Institute of Health and Care Excellence
NFT	NHS Foundation Trust
NHS	National Health Service
NICE	National Institute for Health and Care Excellence
NIHR	National Institute for Health Research
NYHA	New York Heart Association
OCTRU	Oxford Clinical Trials Research Unit
PASDAS	Psoriatic Arthritis Disease Activity Score

OPTIMISE_Protocol_V5.0_17Jun2022.docx

Clinical Research Protocol Template version 15.0

 $\ensuremath{\mathbb{C}}$ Copyright: The University of Oxford and Oxford University Hospitals NHS Foundation Trust 2019

PASI	Psoriasis Area Severity Index
PSAID	PsA impact of disease
Ы	Principal Investigator
PIL	Participant/ Patient Information Leaflet
PIC	Participant Identification Centre
PsA	Psoriatic arthritis
PSP	Priority setting partnership
RA	Rheumatoid arthritis
REC	Research Ethics Committee
RGEA	Research Governance, Ethics & Assurance
RNA	Ribonucleic acid
SMC	Scottish Medicines Consortium
SOP	Standard Operating Procedure
SPARCC	Spondyloarthritis Research Consortium of Canada
ТВ	Tuberculosis
Th17	T helper cells with 17 signature
TNF	Tumour necrosis factor
TNFi	Tumour necrosis factor inhibitors
UKCRC	UK Clinical Research Collaboration
U&E	Urea and electrolytes
VAS	Visual analogue scale
WS	Work stream
WPAI	Work productivity and activity impairment

5. BACKGROUND AND RATIONALE

Psoriatic arthritis (PsA) is an inflammatory arthritis that occurs in ~15% of people with psoriasis, affecting around 150,000 people in the UK¹. Two-thirds of people with PsA suffer joint damage with associated disability ² similar to rheumatoid arthritis (RA) ³. PsA is associated with reduced life expectancy ⁴ and average direct healthcare costs of £2,400 per patient with indirect costs of >£8,000 annually ⁵.

The current treatment of PsA follows a 'step up' 'trial-and-error' approach using different conventional disease-modifying anti-rheumatic drugs (DMARDs) followed by biologics if patients do not respond ¹⁶. Approximately 50% of patients require biologic therapy ⁷. The current first line biologic treatments for PsA target two main immunological pathways:

- 1. Tumour necrosis factor inhibitors (TNFi) monoclonal antibodies or receptor antagonists blocking the action of TNF, a key predominantly myeloid-derived cytokine involved in immune cell trafficking and maintenance of the inflammatory response.
- 2. Interleukin (IL) 17 inhibitors monoclonal antibodies targeting IL-17A which plays a pleotropic role in inflammation including recruitment of neutrophils and bone erosion⁸.

Response rates to both drugs are similar with around 60% of patients achieving a minimal response. However, 50% fail to achieve the therapeutic target of treatment defined by the minimal disease activity (MDA) criteria^{9 10}. Patients not achieving MDA have worse quality of life, ongoing joint damage, functional impairment and high impact on their participation and ability to work ¹⁰. In clinical practice, biologic therapies require use for a minimum of 12 (TNFi) or 16 weeks (IL-17Ai) before response can be evaluated¹⁶ and MDA is assessed even later (24 weeks)¹¹. For patients this means a long delay on a therapy that may never work.

Whilst having different therapeutic options is welcome, there is currently no evidence to guide biologic choice in PsA. We know that some people who fail to respond to a first line biologic will have a good response when they switch to a drug with a different mechanism of action¹² suggesting that disease pathogenesis varies between individuals. Currently we cannot predict who will respond to each therapy resulting in delays on ineffective therapies associated with negative impact on patients' lives and a high cost burden to the NHS.

Currently in clinical practice we select either TNF or IL-17A inhibitors for patients with moderate-severe active PsA based on a limited clinical phenotype (differentiation in psoriasis has been shown), comorbidities, personal experience and cost. In the UK, most patients currently receive TNF inhibitors first line, presumably due to longer term data, physician familiarity and lower cost using biosimilars. However, the Th17 pathway is significantly upregulated in PsA. Th17 cells are a subset of pro-inflammatory T helper cells defined by their production of IL-17, thus suggesting that treatment with IL-17 inhibitors in some individuals could improve outcomes. The lack of data informing the choice of biologics is frustrating for clinicians and for patients who want to know which therapy would be best for them. There has not been a James Lind priority setting partnership (PSP) for PsA however in the recent Psoriasis PSP the question "What factors predict how well psoriasis will respond to a treatment?" was ranked 3rd in the top ten unmet needs. This highlights the importance that both patients and clinicians ascribe to the issue.

It is increasingly recognised that to optimise quality of life and functional ability, treatment should be focused on achieving a treatment target, such as MDA. Patients who achieve MDA have less joint damage as measured using x-rays, better quality of life and function¹⁰. Thus optimising an individual's

OPTIMISE_Protocol_V5.0_17Jun2022.docx

Clinical Research Protocol Template version 15.0

© Copyright: The University of Oxford and Oxford University Hospitals NHS Foundation Trust 2019

Page 14 of 43

outcomes, requires the ability to predict which biologic has the greatest chance of that individual achieving MDA and then utilising this precision medicine approach in routine clinical practice.

This study will test the hypothesis that activated Th17 cell levels can predict response to therapy and elucidate the mechanistic basis of this approach. This study is using two different proven PsA therapies with extensive data from phase 2-4 clinical trials. The primary clinical outcome is a recommended target of treatment in PsA with confirmed prognostic ability. The biomarker used for stratification in this study has proof of concept in a small RCT from Japan¹³, but has been refined using UK patient data to account for potential genetic differences from the Japanese population. In addition to the principal biomarker, a number of additional biomarkers with supportive data from ex-vivo studies will be tested using novel bioinformatic approaches which have proven successful in other immune-mediated inflammatory conditions This data will provide modelled proof of clinical effectiveness for a precision medicine approach to prospectively select biological therapies in individuals with PsA. This approach could easily be implemented into routine NHS practice as both drugs are already NICE approved for use in PsA. Transforming our treatment algorithms in PsA getting the right drug to the right patient the first time will result in rapid control of inflammation, resulting in improvements in patients' function, work participation and quality of life. Optimising drug selection will also provide cost savings to the NHS avoiding unnecessary primary non-response to therapies.

Objectives	Outcome Measures	Timepoint(s) of evaluation of this outcome measure (if applicable)
Primary Objective To compare the response in participants with a high baseline CD4 T cell activated Th17 immunophenotype, compared to those with low baseline proportions on the clinical response to TNF and IL-17A inhibitor therapy in PsA.	Clinical response as measured by the minimal disease activity (MDA) criteria	Immunophenotype data at baseline and clinical response at week 24.
Secondary Objectives To compare the response in participants with high intracellular IL-17 levels, compared to those with low levels on the clinical response to TNF and IL-17A inhibitor therapy in PsA.	Clinical response as measured by the minimal disease activity (MDA) criteria	Immunophenotype data at baseline and clinical response at week 12/16 and week 24.

6. OBJECTIVES AND OUTCOME MEASURES

To understand if the activated Th17 surface and intracellular signature resolves after treatment with IL-17A blockade and how it is altered after TNF blockade.	Activated Th17 proportion and intracellular levels of IL-17	Immunophenotype data at baseline and week 24.
To understand if changes in the activated Th17 surface and intracellular signature differ in treatment responders and non- responders.	Clinical response as measured by the minimal disease activity (MDA) criteria.	Clinical disease pattern and Immunophenotype data at baseline and clinical response at week 12/16 and week 24.
To explore if the immune subset- specific transcriptomic signature can be used to predict response to IL-17A and TNF blocking therapies either alone or in combination with the activated surface and intracellular Th17 signatures.	Clinical response as measured by the minimal disease activity (MDA) criteria.	Clinical disease pattern and Immunophenotype data at baseline and clinical response at week 12/16 and week 24.
To explore if any of the baseline immune signatures are associated with response in different PsA tissues	Clinical response in PsA tissues including joint counts, enthesitis, dactylitis, skin and nail disease and in overall disease as measured by the PASDAS.	Immunophenotype data at baseline and clinical response at week 12/16 and 24.
To explore if any of the baseline immune signatures are associated with response and disease impact from the patients' perspective	Response as measured by patient reported outcomes including PsAID, SF36 and WPAI	Immunophenotype data at baseline and clinical response at week 12/16 and 24.
To use the immune subset- specific transcriptomic signature to identify a limited number to of transcriptomic biomarkers that can be validated in whole blood.	Cell specific transcriptomic data and whole blood transcriptomes	Immunophenotype data at baseline and week 24.
To use the immune subset- specific transcriptomic signature to define the pathways driving biologic-refractory disease.	Cell specific transcriptomic data and whole blood transcriptomes	Immunophenotype data at baseline and week 24.

OPTIMISE_Protocol_V5.0_17Jun2022.docx

Clinical Research Protocol Template version 15.0

 $\ensuremath{\mathbb{C}}$ Copyright: The University of Oxford and Oxford University Hospitals NHS Foundation Trust 2019

Fundamente ma Obligation		
Exploratory Objectives	Clinical response as measured by	Clinical disease pattern and
To use machine learning and	the minimal disease activity (MDA)	Immunophenotype data at
predictive modelling to combine	criteria.	baseline and clinical
baseline clinical phenotypic		response at week 24.
markers such as disease duration		
and clinical expression of disease		
with additional		
immunophenotypical		
(intracellular CD4 Th17		
frequency, CD8 Tc17 frequency,		
MAIT cell frequency, immune		
transcriptomic signature) factors		
to develop a predictive model		
for response to IL-17A and/or		
TNF inhibitor therapy in PsA.		
To compare the response in	Clinical response as measured by	Immunophenotype data at
participants with a high baseline	the minimal disease activity (MDA)	baseline and clinical
CD4 T cell activated Th17	criteria	response at week 12/16.
immunophenotype, compared to		
those with low baseline		
proportions on the clinical		
response to TNF and IL-17		
inhibitor therapy in PsA.		
To explore if the change or	Clinical response as measured by	Immunophenotype data at
absolute levels of activated Th17	the minimal disease activity (MDA)	baseline and 4 weeks and
surface and intracellular	criteria.	clinical response at week
signature or the transcriptomics		12/16 and 24.
at week 4 can predict response		
to IL-17A and TNF blocking		
therapies		

7. STUDY DESIGN

This is an open-label multi-centre, parallel-group, biomarker-stratified two arm randomised controlled trial recruiting adults (≥18 years old) with psoriatic arthritis confirmed by the CASPAR criteria who are planning to start biological therapy for their PsA following routine clinical practice. It will be performed within rheumatology departments at the participating hospitals within the NHS, with sample analysis taking place at associated University research facilities at the University of Oxford, King's College London, and University of Glasgow.

A total of 424 patients eligible for treatment with their first biologic for PsA as part of their standard NHS care will be approached for inclusion. All patients will be required to fulfil the NICE/SMC or the local guidelines for eligibility for biologics in PsA which include the failure of ≥1 conventional DMARDs and the OPTIMISE_Protocol_V5.0_17Jun2022.docx

Clinical Research Protocol Template version 15.0

© Copyright: The University of Oxford and Oxford University Hospitals NHS Foundation Trust 2019

Page 17 of 43

presence of active disease with a minimum of 3 tender and 3 swollen joints. Following consent, patients will undergo a baseline clinical assessment and blood will be taken for immunophenotyping. We will record the therapy that was planned by the physician if they had not been recruited to the trial, prior to their randomisation to be used in subsequent modelling to estimate the additional benefit of any precision medicine test developed. Each participant will be in the study for a maximum of 30 weeks (max 6 weeks screening to baseline and 24 weeks treatment and follow up). During this time, there will be 3 or 4 study visits. All participants will attend once for screening and twice for follow up, with participants at the hub sites attending an additional visit for sample collection. Composite clinical outcome measurements will be collected via an electronic CRF to assess response to treatment. These will include validated questionnaires of disease activity and impact and clinical assessments of disease activity by a member of the study staff. To avoid bias from treatment class, the primary clinical measures will be assessed by a blinded member of the study team. The baseline immunophenotype data will be blinded from all clinical study site personnel, while laboratory staff will be blinded to the allocated therapy. Trial office staff not directly involved with patient care will be unblinded and will enter immunophenotype results into the randomisation system. This will ensure that the primary research question is answered based on blinded data and therefore the open label treatment does not represent a risk of bias.

8. PARTICIPANT IDENTIFICATION

8.1. Study Participants

The population targeted are adults (≥18 years old) with psoriatic arthritis confirmed by the CASPAR criteria who are planning to start biological therapy for their PsA following routine clinical practice.

8.2. Inclusion Criteria

All participants should fulfil the following:

- Participant is willing and able to give informed consent for participation in the study
- Male or female, Age 18 years or over
- Diagnosis of PsA confirmed by the CASPAR criteria [30]
- Is eligible and planned to have biologic therapy for psoriatic arthritis using local guidelines or using NICE/SMC criteria (failure of ≥1 csDMARDs and ≥3 tender AND ≥3 swollen joints).

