9.7. Baseline Assessments

Baseline clinical assessments and questionnaires will be completed at the screening visit and will be used to measure pre-treatment disease activity.

Following the screening visit, eligibility will be confirmed for the study and randomisation will be performed as outlined in section 9.4. The patient will be informed of the drug that they have been randomised to and a routine NHS prescription for that drug (either adalimumab or secukinumab) will be submitted by the clinical care team. Treatment will be started following standard NHS procedures (which usually takes 3-4 weeks from the prescription being written). In most cases, this will mean that NHS drug supply will be delivered to the patient by an approved healthcare delivery company to ensure temperature control. The patient will be trained how to perform the injections themselves and how to safety dispose of any sharps as per usual practise at each participating site. This may be done by telephone or video call as per usual practise at each participating site. The patient will administer the treatment themselves.

The baseline date will be the date that the drug is first administered.

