11.2. Description of the Statistical Methods

The primary clinical response outcome will be the achievement of the MDA criteria. This is a dichotomous composite criteria including clinical outcomes (tender joint count, swollen joint count, enthesitis count and psoriasis score) and patient reported outcomes (patient global score, patient pain score and function measured by the HAQ. To be classified as being in MDA, patients must achieve 5 or more of the criteria given below:

Domain	Measure Used	Criteria for assessing MDA
Peripheral arthritis	Tender joint count (68)	≤1
Peripheral arthritis	Swollen joint count (66)	≤1
Enthesitis	Enthesitis count (LEI and SPARCC)	≤1
Psoriasis	PASI	≤1
Pain	Patient pain VAS	≤15mm
Global disease activity	Patient global VAS	≤20mm
Function	HAQ	≤0.5

The proportion of patients achieving the criteria in the Th17 high vs Th17 low groups will be compared within treatment arms. Primary analysis will be logistic regression adjusted for Th17 as a binary indicator, treatment and an interaction between the 2. We will also adjust for the stratification factors study centre and psoriasis severity. A random effect will be included to account for any heterogeneity in the response due to recruitment centre, with the other variables being incorporated as fixed effects. Primary focus is on the interaction between biomarker and treatment, we will report the p-value for this

OPTIMISE_Protocol_V5.0_17Jun2022.docx

Clinical Research Protocol Template version 15.0

© Copyright: The University of Oxford and Oxford University Hospitals NHS Foundation Trust 2019

interaction and consider a p-value < 0.05 as significant. We will report the mean response rate by treatment and also for each of the 4 strata defined by treatment and biomarker along with 95% CI. Analysis will be on an intention to treat basis, that is according to group randomised to irrespective of compliance with treatment allocation.

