We have given the power for various scenarios. However, head to head comparisons of the 2 drugs have shown no efficacy difference, with a response rate of around 50% for both drugs. We are therefore not interested in a treatment effect per se, it is the interaction between these 2 drugs and the biomarker that will have the potential to personalise treatment that is the aim of this trial. Given that we see no difference in treatment effect in head to head comparisons, an increase in response for patients with high Th17 treated with IL17Ai would presumably imply an increase in response for patients with low TH17 treated with TNFi. Increasing response rates in both these scenarios to 60% would be important, and this we are powered to detect 98% of the time. We are also able to detect a smaller increase in response rate of five percent 84% of the time.

Although we have lower power to detect an increase in response rate in only one of the arms, it is the interaction that is our primary focus and this we are powered to detect. We will incorporate an interim review of the data by the independent DSMC to ensure that the assumed response rates overall are as expected.

Probability of respons	Power (%)	
IL-17Ai	TNFi	
0.5/0.5	0.5/0.5	4.86
0.4/0.6	0.5/0.5	50.14
0.4/0.6	0.55/0.45	83.68
0.4/0.6	0.6/0.4	98.06
0.4/0.6	0.45/0.55	16.24
0.4/0.6	0.4/0.6	5.19

Based on a sample size of 388 and 10,000 simulations

A recently published open-label head to head study of a TNF inhibitor versus an IL-17A inhibitor reported a slightly lower response rate (48 vs 35%)²⁶. We expect a higher achievement of MDA in our study as our patients will have lower baseline active joint counts and psoriasis severity compared to those recruited into this large pharmaceutical sponsored RCT. However even if our response rates are lower (30% vs 50%, rather than 40% vs 60%) our sample size is sufficient to maintain a 95% confidence level and 80% power.

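### Sections 7 and 8.2 disagree on whether the joint minimum covers the local-guideline route, and no criterion requires a patient to be out of MDA at screening

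*Protocol*

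**What the plan says.** **Eligibility.** Protocol section 7 states: "All patients will be required to fulfil the NICE/SMC or the local guidelines for eligibility for biologics in PsA which include the failure of" at least one conventional DMARD and the "presence of active disease with a minimum of 3 tender and 3 swollen joints". As written there, both guideline routes carry the joint minimum. Section 8.2, the operative criterion, asks that the patient be eligible and planned for biologic therapy "using local guidelines or using NICE/SMC criteria (failure of ≥1 csDMARDs and ≥3 tender AND ≥3 swollen joints"). There the bracket follows NICE/SMC only. Section 9.3 allows no exceptions on eligibility. Neither 8.2 nor 8.3 mentions MDA.

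**Endpoint.** Section 11.2 defines the primary outcome: "To be classified as being in MDA, patients must achieve 5 or more of the criteria given below". The seven items are tender joints ≤1, swollen joints ≤1, enthesitis ≤1, PASI ≤1, pain ≤15 mm, patient global ≤20 mm and HAQ ≤0.5. It is a state at week 24, not a change from baseline, and the objectives in section 6 call it clinical response.

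**Baseline data and model.** Section 9.7 says: "Baseline clinical assessments and questionnaires will be completed at the screening visit and will be used to measure pre-treatment disease activity". Section 9.3 lists every MDA component at that visit, so MDA status can be derived before randomisation. Besides Th17, treatment and their interaction, the primary model has these covariates: "We will also adjust for the stratification factors study centre and psoriasis severity". Baseline MDA is not among them.

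**The concern.** There are two linked problems.

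1. A site that follows 8.2 literally may enrol a patient by the local-guideline route with fewer than 3 tender or 3 swollen joints. A site that follows section 7 may not. The enrolled population then depends on which section is read.
2. The trial asks whether Th17 level predicts response to one drug or the other. A patient in MDA at screening who is still in MDA at week 24 counts as a responder on either drug and at either Th17 level, so says almost nothing about that question. Such patients raise all four cell rates and pull the Th17-by-treatment contrast towards zero.

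A later analysis can describe the second problem but cannot change who was enrolled. Eligibility is fixed in the protocol.

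**Working it through.** **1. Ways to be in MDA at entry.** Meeting at least 5 of 7 items is possible in C(7,5) + C(7,6) + C(7,7) = 21 + 7 + 1 = 29 combinations. A patient with at least 3 tender and at least 3 swollen joints fails both joint items (each needs ≤1). Only one combination is then left: all five other items met. So the joint minimum closes 28 of 29 paths, and the local route as worded in 8.2 closes none.

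**2. Reproducing the protocol's power.** Inputs from section 11.3: 388 analysed, 50:50 Th17 split and 1:1 allocation, hence 388/4 = 97 per cell; two-sided 5%; response for low/high Th17 of 0.4/0.6 on IL-17Ai and 0.6/0.4 on TNFi. The check is a Wald test of the difference of two log odds ratios, without the covariates or the centre effect.

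- δ = [logit(0.6) − logit(0.4)] − [logit(0.4) − logit(0.6)] = 4 × 0.4055 = 1.622
- SE = √Σ 1/(97·p(1−p)) = √(4 / (97 × 0.24)) = 0.4145
- z = 3.913; power = Φ(3.913 − 1.960) = 97.5%

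The protocol states 98.06%. For its 0.55/0.45 TNFi row the same formula gives 83.8% against 83.68% stated. All six rows agree within 1 point.

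**3. Adding patients already in MDA.** Let f be their share and q their chance of MDA at week 24, equal in all cells. Each cell rate p becomes (1 − f)p + fq, so the difference of differences becomes (1 − f) times its design value, whatever q is. For example, 0.40 becomes 0.36 at f = 10%. The protocol gives neither f nor q. The table assumes q = 0.9; q = 0.8 and q = 1.0 give results within 1 point.

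| f | Cell rates replacing 0.40/0.60 | Power, 0.6/0.4 TNFi | Power, 0.55/0.45 TNFi |
|---|---|---|---|
| 0 | 0.400/0.600 | 97.5% | 83.8% |
| 2% | 0.410/0.606 | 97.0% | 82.3% |
| 5% | 0.425/0.615 | 96.1% | 80.0% |
| 10% | 0.450/0.630 | 94.3% | 75.9% |
| 20% | 0.500/0.660 | 88.8% | 66.6% |

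Worked row, f = 10%: δ = 2 × [logit(0.63) − logit(0.45)] = 1.466; SE = 0.4144; z = 3.537; power = Φ(1.577) = 94.3%.

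**4. Type I error.** Simulating the null with f = 0, 10% and 20% gave a rejection rate of 5.0% each time. The effect is dilution, not false positives.

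**The case against.** - **Section 7 does set a joint minimum for everyone, and every patient must be eligible and planned for a biologic.** This stands. A reader might infer that nothing keeps patients in MDA out of the trial. The protocol does not support that: where the minimum applies, one narrow path remains.
- **No local guideline text is in the protocol, and no baseline MDA rate is given.** This stands too. A reader might conclude that some week-24 responders will have needed no response at all. That is possible but not shown. The one hint is the sponsor's statement: "We expect a higher achievement of MDA in our study as our patients will have lower baseline active joint counts and psoriasis severity" than in the cited head-to-head trial. It means f cannot be presumed zero, but does not make it large.
- **The 40% and 60% rates are stated for participants as enrolled, so f may already be inside them.** If so, power is unchanged and the table does not apply. The 20-point difference would then need a larger one among patients not in MDA at entry: 0.20/0.9 = 22.2 points at f = 10%.
- **A large f is not credible.** Agreed. At f = 20% the overall rate would be (0.50 + 0.66)/2 = 58% against the protocol's roughly 50%. That row only bounds the range.
- **The DSMC reviews overall response rates, blinded, about half-way.** This could flag a large f but not a moderate one. At f = 10% and q = 0.9, a 45% rate in the other patients gives 0.9 × 0.45 + 0.1 × 0.9 = 49.5% overall, which looks as planned.
- **A sensitivity analysis belongs in the SAP.** The SAP is not at hand and may contain one, so its absence from the protocol is not criticised. The entry criteria are protocol matter.

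**Conclusion.** The point holds in two parts. First, sections 7 and 8.2 contradict each other on whether the joint minimum covers the local-guideline route, and both are current text. Second, no criterion requires a patient to be out of MDA at screening, although the endpoint is the MDA state and the data to check it are collected before randomisation.

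The likely harm is modest. At f up to 5% the main scenario loses at most 1.4 points of power (97.5% to 96.1%) and the weaker one 3.8 (83.8% to 80.0%). Above 5% the weaker scenario falls below 80%. These figures rest on an assumed f, on week-24 MDA among such patients being the same in all cells, and on the design rates applying only to patients not in MDA at entry. Absolute MDA rates would read high as measures of drug response. The interaction test remains valid at 5%.

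**What to change.** 1. Reconcile section 7 with 8.2 so that both say the same about the 3 tender and 3 swollen joint minimum on the local-guideline route. Which way is for the sponsor to decide.
2. Add to 8.2 or 8.3: *not in MDA (fewer than 5 of 7 criteria met) at the screening visit*, computed from the screening eCRF before randomisation.
3. Keep anyone already randomised while in MDA in the intention-to-treat analysis. Report screening MDA by treatment and Th17 stratum, and run the primary model without these patients as a sensitivity analysis, if the SAP does not already do so. Screening MDA is a pre-randomisation variable, so this restriction does not break the randomised comparison.

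The cost is a protocol amendment, with approval under section 16.2 if it is substantial, an eCRF check on data already collected, and a few screened patients made ineligible. Planned recruitment began in January 2022, before this version of 17 June 2022, so the new criterion may not cover everyone; step 3 deals with those patients.
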